The lack of safe and effective pharmacological treatments for MA use disorders is a critical barrier to improved treatment outcomes. This proposal builds on the published translational findings of reduced PCr[22] and NAA [34, 124] levels in MA use disorders, and the clinical and neuroimaging findings from our preliminary study of creatine for MA-using females. At the same time, it follows the recommendation of experts – including NIDA Director [name] and the eminent substance abuse researcher [name] – that strategies outside the brain dopamine reward system be adopted [56, 125, 126]. Achievement of these *Specific Aims* would validate the notion of neuroprotective agents as potential treatments for MA addiction [15], and in particular those which are also capable of improving mood/anxiety and cognitive symptoms. Incorporating pre- and post-treatment imaging into studies of substance misuse can facilitate identification of the neural predictors and correlates of effective MA treatment [127]. Because the effects of drug use on brain function impede patients' ability to benefit from treatment, studies of drug-related alterations in neurobiology utilizing translational study designs are warranted [127]. Thus, we propose an 8-week, randomized, placebo-controlled trial of creatine for females with MA addiction.

Specific Aims for this proposal are: **1. To define the extent of restoration in bioenergetic dysfunction and neuronal viability following creatine supplementation in female MA users.** We hypothesize that creatine will be superior to placebo in the degree of improvement in PCr and NAA levels, measured with ^{31}P -MRS and ^1H -MRS. Changes to the glutamine/glutamate ratio and GABA will be assessed in an exploratory manner. **2. To assess creatine's antidepressant/anxiolytic effect in female MA users.** We hypothesize that creatine will be

superior to placebo in reducing Hamilton Depression Rating Scale (HAMD) and Beck Anxiety Inventory [97] scores. 3. To Measure the Degree of Cognitive Improvement Associated with Creatine in Female MA Users. We hypothesize that creatine will be associated with greater improvement in cognitive function tests, compared with placebo. In addition to these Specific Aims, we will examine urine drug testing results in an exploratory manner, to determine whether creatine vs. placebo is associated with a greater number of MA-free tests

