In addition to these **Specific Aims**, we will monitor subjects' MA use, as improvements in brain bioenergetics, mood/anxiety and may decrease MA usage. Therefore, we will record urine drug testing results, to determine whether creatine vs. placebo is associated with a greater number of MA-free tests during the 8 weeks of randomized treatment.

PARTICIPANT SELECTION CRITERIA

123 women will be randomly assigned in a 1:1 ratio to either creatine or placebo for eight weeks. Table 1 outlines eligibility criteria.

TABLE 1 INCLUSION AND EXCLUSION CRITERIA

INCLUSION CRITERIA:

- Female gender, ages 18-55 inclusive
- Current primary diagnosis of MA dependence or abuse, with MA preferred drug of abuse (Lifetime MA use > 20 grams)
- Current diagnosis of Major Depressive Disorder (MDD)
- Current HAMD score ≥ 10
- Clinical Global Impressions–Severity (CGI-S) depression score ≥ 4
- If taking a psychotropic medication for depressed mood, regimen must be stable for ≥ 4 weeks prior to randomization

EXCLUSION CRITERIA:

- Persons unable to provide adequate informed consent
- Persons who are at clinically significant suicidal or homicidal risk
- Primary substance-related diagnosis *other than* MA dependence or abuse
- Comorbid substance dependence diagnosis, other than nicotine (substance abuse diagnoses are not excluded)
- Positive pregnancy test, due to the unknown effects of MRI scanning on the unborn fetus
- Positive test for antibody to the Human Immunodeficiency Virus (HIV)
- History of renal disease
- Clinically significant medical or neurological illness identified by history, physical exam and laboratory testing
- Known or suspected intellectual disability, or developmental disorder, e.g. autism
- History of hypersensitivity reaction to creatine

WITHDRAWAL / EARLY TERMINATION CRITERIA:

- Withdrawal of informed consent
- Suicide attempt
- Psychiatric hospitalization
- Onset of bipolar disorder or psychotic disorder
- Positive pregnancy test
- Incarceration
- Inability to comply with study protocol

▪ Treatment with electroconvulsive therapy (ECT)▪ Increase in HAMD score > 25% from baseline▪ Serious adverse event

▪ HEALTHY CONTROL SUBJECTS:
 
▪ Female gender, ages 18-55 inclusive▪ No current or past DSM-5 diagnosis, as determined by clinical and structured interviews▪ No first-degree relatives with known or suspected DSM-5 diagnosis

DESIGN

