The proposed study will use a randomized, double-blind, placebo-controlled design. 123 participants will be randomly assigned in a 1:1 ratio to placebo or 5 grams of daily creatine treatment for eight weeks. We also plan to recruit 24 age-matched females (18-55).

STUDY PROCEDURES

All procedures performed by study personnel are research-related. None of the study activities will be considered standard of care. There will be no cost to study subjects for their participation. Participants will be compensated for their time and travel. Table 2A and 2B outlines the schedule of study procedures for treated participants and healthy controls.

Consent will be obtained before any study procedures are initiated. Potential participants will be informed of the study and offered a consent form to review. They will be encouraged to discuss study participation with their relatives. If a potential participant expresses interest in study participation, the informed consent process will be conducted. After the informed consent process, individuals will be offered time to consider study participation and to ask questions. Subjects and parents/guardians will have the opportunity to discuss the study with a study team member in a setting free of coercion. The language of the informed consent form is written at a level easily understood by the subject and any questions asked by the subject will be answered honestly and free of bias. A specific meeting time will be set up between a study team member and the participant where the entire informed consent document will be carefully explained in its entirety. The length of the meeting will be designed so there is the necessary amount of time for all questions to be answered.

Randomization of participants to the two treatment conditions will take place according to a randomization list generated prior to the start of recruitment. 47 (50%) will be randomized to placebo. The study will be conducted as a double-blind trial, with neither participants nor research staff aware of participant assignment. Except in cases of medical emergency, the double-blind will not be "broken" until recruitment is closed and the final participant has completed 8 weeks of treatment with investigational drug. There is no "washout period" for any participant in this study, and participants randomized to placebo will continue treatment with a psychotropic medication throughout their time in the study.

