At the screening visit, an ECG will be conducted in order to examine the heart and ensure participant safety; an adult cardiologist will also evaluate all individuals during the screening phase. If during the MRI/MRS scans we unexpectedly discover something that warrants further inspection, we will refer the participant to her primary care provider for follow-up, along with the MRI/MRS report that shows the findings. Any costs related to following up on unexpected findings will be the responsibility of her and/or her insurance provider. In conjunction with the brain scans performed pre- and post-treatment, a brief battery of cognitive tests will be administered, to evaluate change associated with creatine or placebo. Trained psychometricians administer tests on the day of scanning. Scoring is done blind to subjects' group status, clinical ratings and imaging results. The cognitive testing battery instruments were

chosen because they are sensitive to frontal lobe integrity: the Wisconsin Card Sorting Task (WCST)[129], the Stroop Color-Word Test[130, 131], and the Wechsler Memory Scale (WMS-IV)[132]. Furthermore, the WCST[133], Stroop Test[134] and WMS-IV [90] each have been associated with performance deficits in MA users.

TABLE 2A Schedule of Procedures for Methamphetamine-dependent Females												
	Screening	Treatment Phase								Follow Up Phase		
Study Week →	-2 to 0^a	1*	2*	3*	4*	5*	6*	7*	8*	9	10	11
Informed Consent, Demographics	X											
Medical History & Physical Exam, ECG	X											
Hematology & Chemistries	X									X		
Phlebotomy for Creatinine Levels	X				X					X		
HIV	X											
Pregnancy Test and vital signs	X	X	X	X	X	X	X	X	X	X	X	X
PRISM Diagnostic Interview	X											
ASI	X									X		
Randomization to Creatine or Placebo	X											
Treatment with Creatine or Placebo		X	X	X	X	X	X	X	X			
Urine Drug Screen / Other Drug Use	X	X	X	X	X	X	X	X	X	X	X	X
Concomitant Medications	X	X	X	X	X	X	X	X	X	X	X	X
Food Frequency Questionnaire	X									X		
Cognitive Tests: WCST, STROOP and WMS-IV (with WASI vocabulary)***	X									X		
Adverse Events		X	X	X	X	X	X	X	X	X	X	X
Treatment Program Attendance	X	X	X	X	X	X	X	X	X	X	X	X
Clinical Scales: HAMD**, BAI**, CGI-S**, C-SSRS	X	X	X	X	X	X	X	X	X	X	X	X

³¹ P-MRS and ¹ H-MRS****	X									X		
*During the 8 Treatment Weeks, MA Subjects Have 2 Study Visits Per Week (separated by \geq 48 hours)												
**Procedure will be collected at one of the twice weekly visits												

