- During the intake and assessment interview, participants may become emotionally upset when asked about their psychiatric history including suicide attempts, or physical and sexual abuse.
- There is a 50% chance that the participant will be assigned to placebo, in which they will not receive creatine.
- Participants may experience discomfort or swelling when blood is drawn for laboratory tests. Rarely, infection can result from blood draws.
- It is possible that the participant's illness could worsen during the study. This could be related or unrelated to the study. Individuals with Major Depressive Disorder are at risk for depression, suicidal ideation, and suicide attempts as part of their illness. If the participant's illness worsens to the point that the study doctor considers them a danger to themselves or others, they will be hospitalized. If the participant is hospitalized they will be withdrawn from the study. In the event of hospitalization, the participant or the participant's insurance company will be responsible for the associated costs.
- It is possible that treatment with creatine will not be effective for the participant's depression, and that study participation will therefore delay the start of effective treatment.
- The researchers will take precautions to safeguard the participant's confidentiality, but it is possible that a breach of confidentiality could occur. A Certificate of Confidentiality has been obtained for this study.
- The participants may experience gastrointestinal discomfort as a result of taking study medication. We recommend taking the study medication with food to reduce possible stomach discomfort.
- MRI/MRS scans do not use ionizing radiation like x-rays or CT scans. Instead, magnetic fields and radio waves are used to take the pictures. There are no known risks related to MRI scans – other than the risk of injury when metallic objects are brought into the scanning room by mistake. Serious injury can occur during an MRI scan to persons who have:
 - Cardiac (heart) pacemakers.
 - Metal clips on blood vessels (also called stents).
 - Artificial heart valves.
 - Artificial arms, hands, legs, etc.
 - Brain stimulator devices.
 - Implanted drug pumps.
 - Cochlear [6] implants.
 - Ocular [118] implants or known metal fragments in eyes.
 - Exposure to shrapnel or metal fillings
 - Other metallic surgical parts.
 - Orthodontic braces on the teeth.
 - Body jewelry or piercings that cannot be removed for the scan.

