Overall Analytic Strategy: The analyses proposed are generalized estimating equations (GEE) regression modeling, which will be used for our longitudinal data analyses with group comparison across treatment visits for the variables of metabolite levels, depression/anxiety symptoms, and cognitive tests. GEE allows robust estimations of standard errors and permits adjustment for time-varying covariates. We assume that measurements made closer in time are more correlated than those made farther apart. Thus, first-order autoregressive structure is assumed. For our repeated measurement data, GEE fits a population-averaged model with working correlation structure to statistically evaluate the time effect of creatine supplementation. We will control for age, other drug abuse, anxiety scores, and tissue partial volume effects in each GEE model. Sidak multiple comparison procedure will be employed to adjust for family wise error (FWE) rate. The Sidak tests make conservative controls of FWE, giving slightly smaller adjusted p-values than the Bonferroni correction.

Overall Power and Sample Size Calculations: For this pilot study, considering a 20% attrition rate, 95 participants will be recruited to achieve a sample size of 75. To determine the minimum effect that would likely be detected with a sample size of 75, a power analysis was performed. Effect for the power analysis was specified as average baseline (over two measures) HAM-D scores compared with average HAM-D scores during active treatment (over eight measures). A gradual onset of effect during active treatment is assumed, starting with an effect of 0 and ending with an effect of 0.5, resulting in an average effect during treatment of 0.25. The effect to be tested was treated as a linear combination of the separate measures (y^*), and a pattern of correlation of 0.5 was used. This generated a standard deviation [105] for y^* that will be different from the within-occasion SD for Y itself. Then the effect magnitude specified was divided by the $SD(y^*)$ to generate an "effective" or de facto effect size, which resulted in an effect size of 1.09 with a power of 0.87.

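### The protocol's statement on background psychotropic treatment covers the placebo arm only and conflicts with Table 1, so the background for the Aim 2 comparison is unclear

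*Combined protocol and SAP*

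**What the plan says.** Four places bear on this point.

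- **Table 1, inclusion criteria:** "If taking a psychotropic medication for depressed mood, regimen must be stable for ≥ 4 weeks prior to randomization". The criterion is conditional, applies to all women before allocation, and sets no rule after randomisation.
- **STUDY PROCEDURES, randomisation paragraph:** after noting that nobody is washed out, it states that "participants randomized to placebo will continue treatment with a psychotropic medication throughout their time in the study". The same paragraph says that neither participants nor research staff know the assignment.
- **Specific Aims, Aim 2:** creatine is hypothesised to be "superior to placebo in reducing Hamilton Depression Rating Scale (HAMD) and Beck Anxiety Inventory [97] scores". Background treatment is not mentioned.
- **Overall Analytic Strategy:** "We will control for age, other drug abuse, anxiety scores, and tissue partial volume effects in each GEE model". Psychotropic use is not in that list, and no stratified randomisation is described.

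Table 2A schedules concomitant medications at screening and in every week from 1 to 11, so the information is collected.

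**The concern.** Every randomised woman has current major depression, and Aim 2 is judged on depression and anxiety scores. Whether she is also taking a drug for depressed mood is therefore a basic descriptor of the comparison. Under Table 1, a woman on no such drug is eligible and may be allocated to placebo, yet the randomisation paragraph has her continuing one. The only sentence about background psychotropics during the eight weeks names a single arm.

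Two things are at stake. A reader of the results could not tell from the protocol whether an Aim 2 effect is that of creatine added to existing treatment or that of creatine over a mixture of treated and untreated women. And a rule written for one arm, if anyone tried to follow it literally, would handle the arms differently.

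**Working it through.** The plan gives no figure on this point, so there is nothing to reproduce. The check is a comparison of the texts, followed by a sizing under stated assumptions.

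**1. The texts side by side**

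| Question | Table 1 | Randomisation paragraph |
|---|---|---|
| Must a woman take a psychotropic? | No, conditional | Presumed, unconditional |
| Which arms? | All women, before allocation | Placebo only |
| Which period? | At least 4 weeks before randomisation | Throughout the study |

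The two agree only if the second is read as applying to women already on a drug, in either arm. The text does not say that.

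**2. Could a placebo-only rule operate?** No. Staff and participants are blinded, so nobody managing a participant knows to whom it applies.

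**3. Size if use is optional in both arms**

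Inputs:
- n = 47 per arm, from the randomisation paragraph. Other parts of the document imply different numbers: 75 analysed gives 37.5 per arm, and 123 randomised gives 61.5.
- p, the share of women on a psychotropic. This is not in the documents; 0.3 to 0.6 is assumed.
- g, the effect of that drug on HAMD in SD units. This is not in the documents; 0.3 is assumed, with a range of 0.1 to 0.5.

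Randomisation makes the expected difference in p between arms zero, so the expected bias is 0.

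SD of the chance imbalance = sqrt(2p(1 − p)/n), at n = 47:
- p = 0.3: sqrt(0.42/47) = 0.095
- p = 0.5: sqrt(0.50/47) = 0.103
- p = 0.6: sqrt(0.48/47) = 0.101

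SD of the resulting shift in the HAMD contrast = g × imbalance SD:
- g = 0.3: 0.3 × 0.095 = 0.028 to 0.3 × 0.103 = 0.031, or about 0.03 SD
- g = 0.1: about 0.01 SD
- g = 0.5: about 0.05 SD

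The choice of n matters little. At p = 0.5 and g = 0.3, 37.5 per arm gives 0.3 × sqrt(0.5/37.5) = 0.035, and 61.5 per arm gives 0.3 × sqrt(0.5/61.5) = 0.027.

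**4. What a covariate could recover.** The share of outcome variance due to psychotropic use is p(1 − p)g². At p = 0.5 and g = 0.3 this is 0.25 × 0.09 = 0.0225, about 2%. It would be less if the baseline score already reflects part of the drug's effect.

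**The case against.** The best defence is that the sentence is only badly drafted. It opens with "There is no 'washout period' for any participant in this study", so the natural meaning is that women already on medication keep it, including those given placebo. To continue a drug presupposes taking one, no section tells women on creatine to stop, and allocation is 1:1 and blinded. On that reading Table 1 is respected, the arms are alike in expectation, and adjustment is not needed for validity. Most of this stands. The sentence still does not say it, and it is the only statement that covers the treatment period.

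Three stronger readings may tempt a reader, and the documents do not support them.

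- **The placebo arm is more heavily medicated, which biases Aim 2 against creatine.** This would need women on placebo to be medicated as a rule while women on creatine are not. The no-washout statement and the blinding make that unlikely, so no bias figure should be attached to the point.
- **Aim 2 has no single comparison.** It has one: creatine against placebo as randomised. Optional background treatment makes it a mixed-background comparison, which is still one comparison.
- **RISKS AND BENEFITS is a third conflicting statement,** because it warns that "study participation will therefore delay the start of effective treatment". That warning is conditional on creatine not working, and it concerns effective treatment. A woman on a stable regimen who still meets the HAMD and CGI-S entry thresholds fits it, so it contradicts nothing.

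**Conclusion.** The conflict between the randomisation paragraph and Table 1 is real and should be corrected. As written, the protocol does not define the background on which the HAMD and BAI comparison is made, and its one statement on the treatment period is tied to an arm that blinded staff cannot identify.

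The statistical consequence is limited. With optional use handled alike in both arms, expected bias is zero and chance imbalance is worth about 0.03 SD on HAMD. The latter rests on an assumed drug effect of 0.3 SD, assumed use of 30 to 60%, and 47 per arm; across effects of 0.1 to 0.5 SD it runs from about 0.01 to 0.05 SD. What remains is a matter of interpretation, with a small gain in precision available. Unequal handling of the arms would be a more serious matter, but the documents do not show that it was intended.

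**What to change.** 1. Reconcile Table 1 and the randomisation paragraph so that the statement on background psychotropic treatment does not depend on assigned arm. Which clinical rule applies is for the sponsor to decide.
2. State in Aim 2 whether the comparison is an add-on or a mixed-background comparison.
3. Add baseline psychotropic use (yes/no), taken from the screening entry under Concomitant Medications in Table 2A, as a prespecified covariate in the HAMD and BAI GEE models, before the blind is broken.

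The cost is a wording amendment and one degree of freedom in each of the two models. No new participants, visits or data items are needed. A new randomisation stratum is not asked for: the protocol has the allocation list generated before recruitment starts, and the covariate meets the need.

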***MA subjects with difficulty scheduling the cognitive testing appointment may be allowed to omit these measures and continue in the study as to not delay treatment and in order to facilitate timely enrollment, which is critical for this population.												
****If an individual is screened and determined to be a good fit for study participation but also has a contraindication to MRI scanning, the principal investigator may allow them into the study, however, they will not be scanned for their safety.												
CGI-S = Clinical Global Impressions-Severity Depression Score; C-SSRS = Columbia-Suicide Severity Rating Scale; HAMD = Hamilton Rating Scale for Depression; BAI = Beck Anxiety Inventory; PRISM = Psychiatric Research Interview for Substance and Mental Disorders; STROOP = Stroop Color Word Test; WCST = Wisconsin Card Sorting Test; WMS-IV = Wechsler Memory Scale; WASI = Wechsler Abbreviated Scale of Intelligence; ASI = Addiction Severity Index.												
^a Screening may happen over the course of 2-3 visits.												

TABLE 2B Schedule of Procedures for Healthy Controls

	Screening									Final Visit
Study Week →	-1 to 0 ^a	1	2	3	4	5	6	7	8	9
Informed Consent, Demographics	X									
Medical History & Physical Exam, ECG	X									
Hematology & Chemistries	X									
Phlebotomy for Creatinine Levels	X									
HIV	X									
Pregnancy Test	X									X
PRISM Diagnostic Interview	X									
Food Frequency Questionnaire	X									X
Urine Drug Screen / Other Drug Use	X									X
Concomitant Medications	X									X
Vital Signs	X									X
Cognitive Tests: WCST, STROOP and WMS-IV (with WASI vocabulary)	X									X
Treatment Program Attendance	X									X
Clinical Scales: HAMD**, BAI**, CGI-S**, C-SSRS	X									X

³¹ P-MRS and ¹ H-MRS	X									X
CGI-S = Clinical Global Impressions-Severity Depression Score; C-SSRS = Columbia-Suicide Severity Rating Scale; HAMD = Hamilton Rating Scale for Depression; BAI = Beck Anxiety Inventory; PRISM = Psychiatric Research Interview for Substance and Mental Disorders; STROOP = Stroop ColorWord Test; WCST = Wisconsin Card Sorting Test; WMS-IV = Wechsler Memory Scale; WASI = Wechsler Abbreviated Scale of Intelligence.										
^a Screening may happen over the course of 2-3 visits.										

RISKS AND BENEFITS TO STUDY PARTICIPANTS

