Statistical Analysis for Specific Aim 3: Cognitive testing data with a repeated measures design will evaluate the cognitive improvement after 8 weeks of creatine supplementation, specifically in executive and working memory deficits, found in MA users. The relative improvements on WCST, Stroop and WMS-IV scores associated with creatine versus placebo will be tested conservatively with the assumption of independence among comparisons. Independent variables include a time variable of "visit" (baseline and 8 weeks of treatment), creatine" (placebo or creatine group), and an interaction term, "creatine \times visit", where a significant interaction will indicate significant differences between treatments. The depression effect will be

tested by stratifying depressed and non-depressed MA users. Power and Sample Size Calculations: Previous reports, meta-analysis, and our preliminary data suggest that the cognitive deficits of MA users have medium-to-large (0.5 to 0.8) effect size, especially in the episodic memory, compared to healthy subjects. Thus, the proposed sample size (n=76) will have enough power (> 80%) based on Cohen's guidelines with adjusted Sidak p-values of 0.0169. [137, 138]

ADMINISTRATIVE RESPONSIBILITIES

Resources:

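### The cognitive-test waiver in Table 2A names no visit: it should cover only the screening tests, and Aim 3's n and power should allow for it

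*Combined protocol and SAP*

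**What the plan says.** In the combined protocol and SAP, Table 2A (schedule for methamphetamine-dependent women) has a row headed "Cognitive Tests: WCST, STROOP and WMS-IV (with WASI vocabulary", marked at screening and at week 9. The triple-asterisk footnote is attached to the row label, not to either mark. It says that women with difficulty scheduling the appointment "may be allowed to omit these measures and continue in the study as to not delay treatment and in order to facilitate timely enrollment". It sets no cap and requires no later test.

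The Statistical Analysis for Specific Aim 3 uses two visits ("baseline and 8 weeks of treatment"), with terms for visit, creatine and their interaction; the interaction is the test of treatment. On size it states: "Thus, the proposed sample size (n=76) will have enough power (> 80%) based on Cohen's guidelines with adjusted Sidak p-values of 0.0169". The effect size behind this comes from the statement that "cognitive deficits of MA users have medium-to-large (0.5 to 0.8) effect size" relative to healthy subjects.

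Overall Power and Sample Size Calculations says "considering a 20% attrition rate, 95 participants will be recruited to achieve a sample size of 75". Participant Selection Criteria says "123 women will be randomly assigned in a 1:1 ratio to either creatine or placebo for eight weeks", and Design repeats 123. For missing values, the data-management section provides only a database code. No rule says how women without cognitive scores enter the Aim 3 analysis.

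**The concern.** The permission is wider than its justification. Avoiding a delay to treatment and speeding enrolment are reasons to waive the screening tests. Neither is a reason to waive a test after eight weeks of treatment.

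The two visits carry different risks. A waiver settled before randomisation cannot depend on the arm, so it mainly costs precision and some generalisability. A test skipped at week 9 comes after randomisation and could be related to treatment or to the woman's condition by then; that could bias the creatine-placebo comparison.

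There is also avoidable loss. If the waiver is taken to cover both tests, a woman who missed only the screening session is not tested at week 9 either, although randomisation makes her week-9 score usable for comparing the arms. Aim 3 is one of the trial's three Specific Aims, and its stated sample size makes no provision for any of this.

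**Working it through.** **1. Where 76 comes from.** 95 × (1 − 0.20) = 76. It is the number retained after attrition, so it assumes that every retained woman is tested. The alpha is the Sidak value for three tests: 1 − 0.95^(1/3) = 0.01695, given as 0.0169.

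**2. The plan's power figure.** Two-sample comparison, 38 per arm, two-sided alpha 0.0169 (sidedness is not stated), noncentral t with noncentrality d × √(n per arm / 2).
- d = 0.8: 0.8 × √19 = 3.49, power 0.85.
- d = 0.5: 0.5 × √19 = 2.18, power 0.40.

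The claim of more than 80% is met at the top of the stated effect range and not at the bottom. The comparisons below use d = 0.8, the case in which the claim holds.

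**3. Effect of waivers on power.** The documents give no waiver rate w, so 10%, 20% and 30% are assumptions. Number tested = retained × (1 − w). For the 123 randomised, retained = 123 × 0.80 = 98.4.

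| Waived | Tested, from 76 | Power, d = 0.8 | Tested, from 98 | Power, d = 0.8 |
|---|---|---|---|---|
| 10% | 68 | 0.80 | 89 | 0.91 |
| 20% | 61 | 0.75 | 79 | 0.86 |
| 30% | 53 | 0.67 | 69 | 0.81 |

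About 69 tested women are needed for 80% power (0.806 at 69, 0.799 at 68). From 76, a waiver rate of roughly 10% therefore uses up the margin. From 98.4, 76 tested women are still reached with up to 1 − 76/98.4 = 23% waived.

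**4. What week-9-only scores recover.** Suppose the waiver is limited to screening and all waived women are tested at week 9. Let r be the correlation between the two visits. The documents give 0.5 for HAM-D and nothing for the cognitive tests, so 0.5 to 0.7 is assumed. Assume also equal variances and missingness unrelated to outcome. Effective n is the number of women tested twice who would give the same precision under the same model.

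- *Separate baseline mean per arm*, as in the Aim 3 model (visit, creatine, interaction). The variance of an arm's estimated change is proportional to [2(1 − r) + (w/(1 − w))(1 − r²)]/N, so effective n = 76 / [1 + (w/(1 − w)) × (1 + r)/2]. For w = 0.2, r = 0.5: 76 / (1 + 0.25 × 0.75) = 64.0.
- *Common baseline mean across arms.* A week-9-only woman carries (1 − r²) of the information of a pair, so effective n = 76(1 − w) + 76w(1 − r²). For w = 0.2, r = 0.5: 60.8 + 15.2 × 0.75 = 72.2.

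| Waived | Complete pairs only | Separate baseline means, r = 0.7 to 0.5 | Common baseline mean, r = 0.7 to 0.5 |
|---|---|---|---|
| 10% | 68 | 69 to 70 | 72 to 74 |
| 20% | 61 | 63 to 64 | 69 to 72 |
| 30% | 53 | 56 to 58 | 65 to 70 |

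Testing waived women at week 9 adds little under the model as written. Most of the gain needs the common baseline mean.

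**The case against.** The strongest reply is that the footnote, read with its own reasons, concerns the screening session only, and that its permission is discretionary. A reader might infer that the sponsor means to let women skip the week-9 outcome test. The documents do not say that. What stands is that a marker on a row with two visits, without a limit, does not exclude it.

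A second reply is that no shortfall has been shown, and this is right as far as it goes. A reader might infer that n=76 assumes every randomised woman is tested, or that Aim 3 will be underpowered because of the waiver. Neither follows: 76 already removes 20% attrition, the waiver rate is unknown, and with 123 randomised the power at d = 0.8 stays above 0.80 at all three assumed rates. The loss in the first half of the power table applies only if the 95 in the power section is the operative number.

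Third, no text says that women without a baseline score are excluded. The plan specifies GEE across visits and no complete-case rule. That is correct, but nothing says they are included either, and whether the waiver covers one test or both is left open.

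Finally, the waiver is not the largest weakness in Aim 3's power. At d = 0.5 power is 0.40 with all 76 tested, and the effect range describes a deficit against healthy subjects, not a creatine-placebo difference. That is a separate matter and does not remove this one.

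**Conclusion.** The point holds in limited form and should be acted on. The waiver names no visit although its reasons apply only before treatment. This leaves open both the loss of all Aim 3 data from a waived woman and the omission of the outcome test after randomisation. The second could bias the arm comparison, but it is a possibility left by the wording; the documents do not show that it is intended or how often it would occur.

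On size, the plan makes no allowance for waivers. Under 95 recruited, assumed rates of 10%, 20% and 30% take power at d = 0.8 from 0.85 to 0.80, 0.75 and 0.67. Under 123 randomised, the same rates leave 0.91, 0.86 and 0.81. The results assume 20% attrition, a two-sided alpha of 0.0169 and the waiver rates shown. The case for correcting the footnote depends on none of these figures.

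**What to change.** 1. Reword the footnote so that the waiver applies to the screening tests only, and offer the week-9 tests to every randomised woman, including those without baseline tests.
2. State that week-9-only scores stay in the Aim 3 analysis, using a model with a common baseline mean across arms. In the GEE this can be done by keeping visit and the creatine-by-visit interaction and dropping the creatine main effect. Keeping the scores without this change recovers little.
3. State how missing week-9 scores will be handled.
4. Reconcile 95, 75 and 76, and the 47 allotted to placebo in Study Procedures, with the 123 randomised. Then restate Aim 3's n and power for the number expected to be tested, with an explicit waiver rate.

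The cost is wording in the schedule and the analysis section. The week-9 tests are already scheduled, and flexibility at enrolment is kept. The stated n or power for Aim 3 may become slightly less favourable.
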